5.7 Statistical Analysis

Overview of statistical analyses for IPT uptake: The target population for the primary outcome is all HIV+ adult (≥ 15 years) patients who are eligible for IPT within 36 months of intervention start (in each pair-matched DHO group), and in care at a facility overseen by DHOs participating in the SPIRIT trial. The analytic population for the primary outcome is all adults in active HIV care in the largest two clinics in each district of the trial. The primary outcome (Section 5.6.1 above) for each randomized group is the rate at which these patients receive a prescription for INH over the 12-36 month period following the intervention start. In the primary analysis, we will account for prior INH starts and changes in the analytic population. All DHO groups are followed for three years total.

Estimation of the impact of the SPIRIT intervention on this outcome will be based on a two-stage analysis. In the first stage we will estimate IPT uptake for each DHO group. IPT uptake will then be compared between SPIRIT intervention and control arms with targeted maximum likelihood estimation (TMLE), adjusting using a pre-specified algorithm, and accounting for the pair-matched design and limited numbers of independent units.⁴² As a secondary analysis, we will implement the unadjusted effect estimator. Hypothesis testing will be based on a two-sided test at the $\alpha=0.05$ significance level. We also propose to examine possible effect modifiers and mediators (e.g. HIV prevalence, TB screening, loss to follow-up rates, study time, drug shortages and drug availability).

Analyses of secondary quantitative outcomes (IPT completion, TB incidence: see Aim 2) will be implemented analogously.

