Effect estimation: To estimate the effect of the SEARCH-IPT intervention on IPT uptake, we will compare IPT incidence rates by arm using a two-stage approach that appropriately accounts for the cluster randomized study design [1]. In Stage 1, the incidence of IPT uptake will be estimated for each district, as described above. Then in Stage 2, uptake will be compared between arms with targeted minimum loss-based estimation (TMLE) [4], adaptively selecting the district-level adjustment variables that optimize precision, while preserving Type-I error control [5, 6]. Specifically, we will use leave-one-out cross-validation to select from the following set of baseline covariates the ones which maximize empirical efficiency: baseline IPT uptake, baseline active care size, or nothing (unadjusted). In secondary analyses, we will implement an unadjusted effect estimator as the contrast in the average IPT uptake between arms.

The primary effect measure will be on the relative scale and for the N districts involved in the study (i.e., the sample rate ratio) [7-11]:

$$\frac{\psi(1)}{\psi(0)} = \frac{1/N \sum_{i=1}^N \alpha_i Y_i(1)}{1/N \sum_{i=1}^N \alpha_i Y_i(0)}$$

where α_i are weights for the district i and $Y_i(z)$ is the counterfactual IPT uptake over the two-years of follow-up if possibly contrary-to-fact district i were in treatment arm $Z = z$. We will test the *null hypothesis* that the SEARCH-IPT intervention did not improve IPT uptake, as compared to standard-of-care, with a one-sided test at the 5% significance level. In secondary analyses, we will examine the effect on the absolute scale: $\psi(1) - \psi(0)$. We will report point estimates and two-sided 95% confidence intervals for the arm-specific endpoints as well as the relative and absolute effects.

Primary analyses will weight the N districts equally: $\alpha_i=1$ for all i . In secondary analyses, we will evaluate the effect at the clinic-level, and in sensitivity analyses, we will weight proportionally to active care size [12].

Primary analyses will include all districts, including those created during follow-up. Secondary analyses will restrict to the original districts, who had the longest exposure to the intervention.

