Statistical inference: Recall that 4-7 districts were put into groups for the purposes of pair-matching and treatment randomization. In the intervention arm, these clusters are the basis for mini-collaborative activities. In the control arm, there are **no** mini-collaborative meetings or any other study activities. Instead, the control condition corresponds with the standard of care. Therefore, it is reasonable to assume districts in the control arm are independent.

Given this independence structure (at the mini-collaborative level in the intervention arm and at the district level in the control arm), we take the following approach to statistical inference. In the primary analysis, we will assume there are 7 independent units corresponding to the mini-collaboratives in the intervention arm, and 40 independent units corresponding to the districts in the control arm (total $N = 47$). In sensitivity analyses, we will treat the randomized cluster as the independent unit (total $N = 14$). In all analyses, we will use the influence function for standard error estimation [11] and the Student's t -distribution with $(N - 2)$ degrees of freedom as finite sample approximation to the standard normal distribution [11].

Primary analyses will break the matched pairs used for randomization. For completeness, we will also conduct a paired t-test ($N = 7/\text{arm}$), implement a permutation test, and also estimate the intervention effect with mixed (random) effects models and with generalized estimating equations (GEE) [13, 14].

Sensitivity analyses: In addition to the sensitivity analyses described above, we will conduct the following sensitivity analyses. To minimize the impact of secular trends, we will exclude the “100-day IPT push” (Q3-2019). To better understand the impact the COVID-19 pandemic which caused a lockdown to be initiated in Q2-2020, we will conduct an analysis excluding the post-lockdown period and an analysis excluding the pre-lockdown period. Given the expected skewed distribution of clinic sizes, we will conduct two sensitivity analyses excluding clinics with baseline active care size exceeding 2500 patients and exceeding 5000 patients.

Subgroup analyses: We will repeat the above analyses within strata defined by sex, baseline active care size (≤ 1000 vs. >1000), and region.

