Effect estimation & statistical inference: To estimate and obtain inference for the effect of the SEARCH-IPT intervention on HIV-associated TB, we will compare the district-level TB incidence rates by arms using an analogous two-stage approach as for the primary outcome. In Stage 1, the incidence of TB diagnoses will be estimated for each district, as described above. Then in Stage 2, district-level incidence will be compared between arms with TMLE to adaptively select from the following set of district-level adjustment variables the ones that optimize precision: baseline TB incidence, baseline active care size, or nothing (unadjusted). In secondary analyses, we will implement the unadjusted effect estimator as the contrast in the average TB incidence rates between arms. We will test the *null hypothesis* that the SEARCH-IPT intervention did not reduce the incidence of HIV-associated TB, as compared to standard-of-care, with a one-sided test at the 5% significance level.

As before, the primary effect measure will be on the relative scale and for the N districts involved in the study (i.e., the sample incidence ratio). In secondary analyses, we will examine the effect on the absolute scale. We will also report point estimates and two-sided 95% confidence intervals for the arm-specific endpoints and effect estimates. Primary analyses will weight the N districts equally, while sensitivity analyses will weight proportionally to baseline active care size [12]. We will use the same approach to statistical inference as the primary endpoint.

Sensitivity analyses: We will also conduct the sensitivity analyses, as specified for the primary endpoint. Here, we will exclude districts whose baseline active care size is $>10,000$ patients and $>20,000$ patients.

Subgroup analyses: We will repeat the above analyses within strata defined by baseline active care size (≤ 5000 vs. >5000), region, and age (pending data availability).

Additional analyses: We will examine how TB incidence varies over time by plotting the quarterly incidence rate (as described above) and the cumulative incidence (quarter-specific number of TB cases divided by quarter-specific number on ART) over time by arm and region. Using analogous methods to the primary endpoint, we will evaluate time trends and the impact of DHO/DTLSSs participation.

Secondary endpoint: Pending data availability, we will repeat the above analyses to examine the SEARCH-IPT effect on TB treatment initiation.

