4 Secondary outcome: Knowledge, attitudes, and practices regarding IPT

To assess mechanisms through which the intervention operates, we will conduct annual quantitative surveys among DHOs and DTLSSs to evaluate changes in their knowledge, attitudes, and practices regarding IPT. Details of these surveys are available elsewhere; here, we focus on the statistical analysis to evaluate change from baseline in familiarity with IPT, knowledge of IPT's health benefits, and practical challenges in TB management. Specific survey questions and their coding are given

in the Appendix.

Data source: Surveys will be administrated to all DHOs and DTLSSs by study staff at the time of randomization and then 1 and 2 years later. Study staff will attempt to reach and survey all participants in both arms.

As an example of a question, consider “*On a scale of 1 to 5, with 5 being very familiar with IPT, and 1, not knowing much yet about IPT, how familiar are you with IPT?*” The possible answers are “1: No knowledge of IPT; 2: Somewhat unfamiliar–low knowledge of IPT; 3: Somewhat familiar; 4: Familiar; 5: Very familiar–high knowledge of IPT”. Thus, the survey questions will elicit Likert-type answers with evenly spaced responses. In line with standard practice for such outcomes , we will evaluate them quantitatively. Specifically, for each district, we will calculate the average response among its representatives at baseline, at year-1, and at year-2.

Effect estimation: To estimate and obtain inference for the effect of the SEARCH-IPT intervention on IPT knowledge/attitudes/practices, we will first calculate a change-outcome as the average response at follow-up minus the average response at baseline in each district. We will then compare these outcomes with the unadjusted effect estimator (equivalent to the Student’s *t*-test) and test the *null hypothesis* of no improvement in IPT knowledge/attitudes/practice, as compared to standard-of-care, with a one-sided test at the 5% significance level.

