For all approaches, we will test the *null hypothesis* of no improvement from the intervention with a one-sided test at the 5% significance level. We will also report point estimates and two-sided 95% confidence intervals for the relative effect, the absolute effect, and the arm-specific mean outcomes. We will also report total completions by arm.

Additional analyses: We will repeat the above analyses within subgroups defined by sex, timing of IPT initiation (before Q3-2019 “100-day IPT push” or during Q3-2019), age group (15-24 years or 25+ years), and marital status (never married, married/living together, divorced/separated/widowed, missing). We will also use an individual-level TMLE to examine predictors of non-completion. We will provide descriptive statistics on the subsample, including their demographics and care outcome (e.g., ARV switches).

Secondary endpoint: We will repeat the above analyses to examine the effect of the SEARCH-IPT intervention on viral suppression, defined as HIV RNA viral level <400 copies/mL.

6 Appendix

6.1 History of changes:

- Version 1.0 was locked on July 18, 2021 prior to unblinding and effect estimation for IPT uptake (the primary outcome), IPT completion among persons starting IPT, and HIV-associated TB incidence.
- Version 2.0 was created to include the pre-specified analysis plan for the quantitative surveys on knowledge, attitudes, and practices regarding IPT. Version 2.0 was locked on September 15, 2021, prior to unblinding and effect estimator for the survey outcomes.
- Version 2.1, this version, was created to correct grammatical errors and other typos. Version 2.1 was locked on November 10, 2021 prior to submission of the manuscript.

6.2 Select survey questions:

[figure not shown]
The following are examples of survey questions, designed to understand the impact of the SEARCH-IPT intervention on IPT knowledge, attitudes, and practices among DHOs and DTLSSs. Full survey materials are available elsewhere.

1. How familiar are you with IPT? With responses: 1: no knowledge of IPT; 2: somewhat unfamiliar – low knowledge of IPT; 3: somewhat familiar; 4: familiar; 5: very familiar – high knowledge of IPT.
2. How strong is the evidence that INH prevents active TB in HIV-infected patients? With responses: 1: very weak; 2: weak; 3: mixed; 4: strong; 5: very strong.

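### The SAP tests IPT uptake, TB incidence and IPT completion one-sided at 5% where the protocol sets a two-sided 5% test, and its 80% power for the primary outcome rests on that choice

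*SAP*

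**What the plan says.** Protocol 5.7, on the primary outcome of IPT uptake: "Hypothesis testing will be based on a two-sided test" at alpha 0.05. The same section then says: "Analyses of secondary quantitative outcomes (IPT completion, TB incidence: see Aim 2) will be implemented analogously".

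The SAP sets a different rule for each of these outcomes:

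- Section 2, IPT uptake: the null is that the intervention "did not improve IPT uptake, as compared to standard-of-care, with a one-sided test at the 5% significance level".
- Section 3, TB incidence: the null is that it "did not reduce the incidence of HIV-associated TB, as compared to standard-of-care, with a one-sided test at the 5% significance level".
- Section 5, IPT completion: the null is one "of no improvement from the intervention with a one-sided test at the 5% significance level".

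Section 4 does the same for the survey outcomes, with a null "of no improvement in IPT knowledge/attitudes/practice, as compared to standard-of-care, with a one-sided test at the 5% significance level". The protocol does not explicitly fix the sidedness of those.

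Next to the one-sided tests the SAP keeps two-sided intervals. Section 2 says "We will report point estimates and two-sided 95% confidence intervals", and Sections 3, 4 and 5 do likewise. The power appendix (6.3) states that it used formulas for one-sided tests. The SAP gives no reason for one-sided testing at 5%, and its history of changes (6.1) does not mention sidedness.

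**The concern.** The decision rule for the primary hypothesis differs between two current documents, and nothing says which one governs. A result favouring the intervention with a two-sided p-value between 0.05 and 0.10 is positive under the SAP and negative under the protocol. The SAP could also declare improvement beside a 95% confidence interval for the rate ratio that includes 1. Total nominal alpha is 5% in both documents; what doubles is the part spent in the direction of benefit. The stated power was computed for the more lenient rule, so it overstates what the design offers under the protocol's rule.

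**Working it through.** **1. The band in which the two rules disagree.** For the primary analysis the SAP states "we will assume there are 7 independent units corresponding to the mini-collaboratives in the intervention arm". With 40 control districts this gives N = 47, and the reference distribution is t with N − 2 = 45 degrees of freedom.

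| Degrees of freedom | One-sided 5% critical t | Two-sided 5% critical t |
|---|---|---|
| 45 (primary analysis) | 1.679 | 2.014 |
| 12 (N = 14 sensitivity analysis) | 1.782 | 2.179 |

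Any t between the two values in a row is a success under the SAP and not under the protocol. If test and interval use the same standard error and t distribution, the 95% interval then includes no effect.

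**2. Reproducing the SAP's 80% power.** Inputs from SAP 6.3: c = 7 groups per arm, k = 0.25, y = 21,500 person-years per group, control rate 0.22, intervention rate 0.32, one-sided 5%, randomization group as the unit. The standard unmatched formula for rates is

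`c = 1 + (z_a + z_b)² × V`, with `V = [(r0 + r1)/y + k²(r0² + r1²)] / (r1 − r0)²`

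- (r0 + r1)/y = 0.54/21,500 = 0.000025
- k²(r0² + r1²) = 0.0625 × (0.0484 + 0.1024) = 0.009425
- V = 0.009450/0.01 = 0.945
- One-sided: c = 1 + (1.645 + 0.842)² × 0.945 = 1 + 6.183 × 0.945 = 6.84, so 7 groups per arm, as the SAP states.
- Power at c = 7: √(6/0.945) = 2.520, and Φ(2.520 − 1.645) = **80.9%**.

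The SAP figure is reproduced.

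**3. The same calculation with the protocol's test.**

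- c = 1 + (1.960 + 0.842)² × 0.945 = 1 + 7.849 × 0.945 = 8.42, so 9 groups per arm for 80% power.
- Power at c = 7: Φ(2.520 − 1.960) = **71.2%**.

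Other two-sided forms of the formula give 77.7% (without the +1), 63.3% (with +2) and 70.5% (noncentral t on 12 degrees of freedom in place of the +1). None reaches 80%.

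**4. The SAP's second scenario.** The control rate is 0.30. The stated 13.5% increase has to be absolute (0.30 versus 0.435): read as relative (0.30 versus 0.3405), one-sided power would be only 22%. With V = 0.959:

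| Rates per 100 person-years | One-sided 5% power | Two-sided 5% power | Two-sided increase detectable with 80% power, 7 per arm |
|---|---|---|---|
| 22 vs 32 | 80.9% | 71.2% | 11.5 |
| 30 vs 43.5 | 80.4% | 70.6% | 15.6 |

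**5. How often the rules disagree.** With no effect, 5% − 2.5% = 2.5% of trials are positive under the SAP only. At the planned effect of 22 versus 32, the share is 80.9% − 71.2% = 9.7%.

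**6. What would restore 80% two-sided power.** Solving for k with c = 7: V must equal 6/7.849 = 0.764, so k² = (0.007644 − 0.000025)/0.1508 = 0.0505 and k = 0.225. Against k² = 0.0625, that is about 19% less between-group variance.

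**The case against.** The strongest reply is that the one-sided rule was pre-specified. SAP version 1.0 was locked before unblinding and effect estimation for all three outcomes, and the history records no later switch. The rule is stated openly in every outcome section and in the power appendix. The hypothesis is directional, and readers will have the two-sided 95% intervals to judge by. All of this is true, and nothing here suggests a post hoc change. But an early lock does not reconcile the SAP with the protocol. Interest in one direction also does not by itself explain why that direction should carry 5% rather than 2.5%, and the SAP offers no argument for it.

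A second reply is that SAP 6.3 calls its calculation conservative, because it takes the randomization group as the unit and ignores covariate adjustment. Actual two-sided power may therefore exceed 71%. That stands as a limit on the power figures. The SAP quantifies no such gain, however, and the point does not touch the conflict over the decision rule.

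Third, the protocol's two-sided rule for TB incidence and IPT completion is inferred from its statement that they are analysed analogously, and the 80% power covers IPT uptake only. Both limits are accepted.

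Finally, version 2.1 was locked shortly before manuscript submission, so an amendment now could follow knowledge of the results; the documents do not say. Returning to the protocol's stricter rule cannot inflate the error in the direction of benefit, even if it is done late.

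**Conclusion.** The concern holds; the SAP's test is wrong as written against the protocol. The two documents give different decision rules for the primary outcome, explicitly, and for TB incidence and IPT completion by the protocol's carry-over. The nominal error in the direction of benefit is 5% rather than 2.5%. The disputed band is t from 1.68 to 2.01 on 45 degrees of freedom, which covers 2.5% of trials with no effect and about 9.7% at the planned effect. Under the SAP's own inputs, the 80% power becomes about 71% with the protocol's test. The power figures and the 9.7% rest on the group-level normal calculation in SAP 6.3, not on the planned TMLE with 47 units. If the observed result lies far outside the band, both rules agree, but the plan should not rely on that.

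**What to change.** - In SAP Sections 2, 3 and 5, make the confirmatory test two-sided at 5% (equivalently one-sided at 2.5%), in line with Protocol 5.7 and the 95% intervals. Use the same rule in Section 4 for consistency, noting that the protocol does not explicitly cover those outcomes.
- Record this as a dated amendment that returns to the protocol's rule, and state whether effect estimates were known at that date.
- If one-sided 5% p-values are also shown, label them supplementary.
- Restate SAP 6.3 along these lines: under the same conservative group-level calculation, before any gain from covariate adjustment or the 47-unit analysis, 7 groups per arm give about 71% two-sided power for an increase of 10 per 100 person-years from 22, and 80% power for an absolute increase of about 11.5 from 22 or 15.6 from 30.

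The cost is a short documented amendment after the SAP lock and a less favourable stated power. No new data are needed.

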The overall study design is a pair-matched cluster randomized trial. In Phase 1, the clusters correspond to groups of DHOs and are pair-matched within region on predictors of the primary outcome (IPT uptake). The primary outcome of IPT initiation as well as key secondary outcomes of IPT completion and TB incidence, and will be measured among providers and patients in facilities overseen by the DHOs. A sub-sample of adults prescribed INH will be followed longitudinally and assessed for adherence, TB incidence, and costing outcomes (Aims 2 and 4). In Phase 2, we will evaluate the impacts of enhanced business training among Phase 1 SPIRIT intervention DHOs from Southwestern Uganda on IPT initiation (Aim 5) and determine the effect of DHO-provided business training (following DHO participation in a training of trainers' curriculum) on the leadership and management skills of the District Health Team (DHT) members they supervise and health outcomes that DHTs oversee in Southwestern Uganda (Aim 6).

5. The SPIRIT Intervention Trial

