9.2. Eligibility criteria

9.2.1. Inclusion criteria

- (a) District Health Officer or District TB Supervisor (or other DHO-appointed TB focal person) from the Phase 1 Southwestern Uganda region which includes 2 intervention and 2 control DHO groups (of 5-10 DHOs/group)
- (b) By definition, the DHO and District TB Supervisors in Uganda are all ≥ 18 years of age

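### Regional subgroup intervals use an N-2 rule although the Southwest has only two intervention mini-collaboratives, so they are likely somewhat too narrow

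*SAP*

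**What the plan says.** SAP section 2 (Statistical inference) assumes "7 independent units corresponding to the mini-collaboratives in the intervention arm" and 40 single districts as independent units in the control arm, so N = 47. All analyses use an influence-function standard error and a t distribution with N-2 "degrees of freedom as finite sample approximation to the standard normal distribution". The effect is tested one-sided at 5% and reported with a two-sided 95% interval.

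Under Subgroup analyses the same section says "We will repeat the above analyses within strata defined by sex, baseline active care size (≤ 1000 vs. >1000), and region". SAP section 3 takes over the same inference for TB incidence and does likewise: "We will repeat the above analyses within strata defined by baseline active care size", with region also listed. Neither section states how many groups each region contains or gives a small-sample rule for strata.

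Protocol section 4 says the clusters were "pair-matched within region on predictors of the primary outcome". Protocol 9.2.1 gives the Southwest "2 intervention and 2 control DHO groups". SAP section 1 has 14 groups, 7 per arm, in three named regions.

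**The concern.** N-2 is a reasonable small-sample device when both arms supply a fair number of units. Within a region they do not. In the Southwest the intervention-arm variance comes from two group residuals that cancel, while the t multiplier is chosen as if that variance were known about as well as the control-arm variance. That makes the interval too short.

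Regional results are likely to be read closely, because region sets the calendar window: follow-up starts in Q1-2019 in the Southwest and Q2-2019 elsewhere. No decision rule rests on them. What is at stake is a regional IPT or TB effect that looks firmer than two mini-collaboratives can support.

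**Working it through.** **1. The plan's own figure.** SAP 6.3 inputs: 22 vs 32 per 100 person-years, k = 0.25, 21,500 person-years per group, one-sided 5%, 80% power. The formula is c = 1 + (z_α + z_β)² [(λ0+λ1)/y + k²(λ0²+λ1²)]/(λ1-λ0)².

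- Bracket: 0.54/21,500 + 0.0625 × (0.0484 + 0.1024) = 0.00945.
- c = 1 + (1.645 + 0.842)² × 0.00945/0.01 = 6.84, rounded up to 7 groups per arm, with power 80.9%.

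The second case, 30 vs 43.5, gives 6.93. The whole-trial figure reproduces. No regional power, N or df is stated.

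**2. Groups per region.** There are 7 pairs and the Southwest has 2, leaving 5 for East and East-Central. If pairs sit within three separate regions, one of these two has at most 2 and the other at least 3.

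**3. Degrees of freedom in the Southwest.** Protocol 1.1 gives 14 districts, so about 7 controls if split evenly. Two groups at the SAP's maximum of 7 would give 14. The district counts do not agree: four groups of at least 4 need 16 or more. Hence a range.

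- N-2 = 2 + 7 - 2 = 7, up to 2 + 14 - 2 = 14.
- Control share of units: 7/9 = 78% to 14/16 = 88%.

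**4. The variance.** For the log rate ratio, SE² = Σ_j (S_j/(n1·ȳ1))² + Σ_i (r_i/(n0·ȳ0))². S_j is the residual sum in mini-collaborative j and r_i a control-district residual. With two groups S_1 = -S_2, one independent piece of information. With a single group S_1 = 0, so the intervention-arm term is exactly zero.

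**5. Null simulation** (40,000 runs). District rates were normal with mean 0.22 and CV 0.4 (assumed). Control districts were independent, and ICC (assumed) applied in the intervention arm only. The estimator was unadjusted; TMLE covariate selection was not simulated. Coverage is scored against a ratio of 1.

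| Intervention groups × districts vs control districts | ICC | 95% CI non-coverage | One-sided error |
|---|---|---|---|
| 2×4 vs 7 | 0.05 | 8.1% | 6.1% |
| 2×4 vs 7 | 0.27 | 9.8% | 7.2% |
| 2×4 vs 7 | 0.5 | 11.1% | 8.6% |
| 2×6 vs 11 | 0.05 | 9.3% | 6.9% |
| 2×6 vs 11 | 0.27 | 12.6% | 9.1% |
| 2×6 vs 11 | 0.5 | 14.8% | 10.6% |
| Whole trial, 7×6 vs 40 | 0.05-0.5 | 6.2-7.7% | 5.8-7.5% |

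The first layout approximates the 14-district Southwest with equal group sizes; the second is assumed. At ICC 0, two-group non-coverage is about 8-9%. Over repeat runs with ICC 0.05-0.5 it is about 8-16%, with one-sided error 6-11%.

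**6. Second parametrisation** (20,000 runs per cell). District variance was scaled to a group-mean CV of 0.25, with 7-14 control districts in the Southwest.

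- ICC 0: one-sided error 5.2-5.9%, coverage 91.3-92.5%.
- ICC 0.1-0.5: one-sided error 6.1-12.9%, coverage from 91.7% down to 82.3%.
- Control districts also clustered, ICC 0.1-0.5: one-sided error 7.1-19.6%.

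**7. Companion analyses within a two-pair region.**

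- Randomized cluster as unit, N-2 = 2 df: size 6.6-8.3%, coverage 91.5-93.0%.
- Paired t-test: 1 df, one-sided critical value 6.3.
- Permutation test that respects the pairs: smallest one-sided p = 1/2² = 0.25. With 3 or 4 pairs it is 0.125 or 0.0625, so it cannot reach 0.05 there either.

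**The case against.** **Estimand.** The SAP targets the sample rate ratio for the districts in the study. A shared effect placed only in the intervention arm gives those districts real treatment effects, so scoring against 1 is not the SAP's target. Scored against the sample ratio at ICC 0.27, with the correlation of a district's two potential outcomes set anywhere from 0 to 1, non-coverage is 3.4-7.1% in the Southwest layout and 4.5-8.6% for 2×6 vs 11. This stands and lowers the claim. It does not remove it: with no effect in any district and ICC 0 the sample ratio is exactly 1, and non-coverage is still about 8-9%.

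**Unknown ICC.** A reader might derive an ICC of 0.27 from k = 0.25, as (6 × 0.0625/0.4² - 1)/5. The documents do not support this. District CV 0.4 is assumed, and SAP 6.3 applies k to randomization groups in both arms. If districts are independent, k = 0.25 with groups of 6 implies a district CV of 0.25 × √6 = 0.61 and ICC 0. The ICC is an assumption throughout.

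**Layout.** A reader might infer one or two intervention groups in every region. Only the Southwest count is stated. A second region with at most two follows only under three-way regional pairing, and Protocol 3.1 speaks of two major regions while naming three. A one-group region is possible but undocumented, so the 15-28% non-coverage simulated for it is hypothetical.

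**Already handled.** Repeating all analyses also carries the cluster-level companions into each region. They help, but they do not lead the inference, and the influence-function version remains mildly liberal.

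**Not unique to regions.** The whole-trial analysis also under-covers slightly. This is the same mixed-unit choice, with a larger effect in small strata.

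**Conclusion.** The point holds in a limited form. In the Southwest, and in one further region if pairing was within three regions, the N-2 rule gives the intervention-arm variance more credit than two mini-collaboratives can bear. At district CV 0.4, two-group intervals miss about 8-9% of the time at ICC 0. Over ICC 0.05-0.5, scored against a ratio of 1, they miss about 8-16% of the time, with one-sided error about 6-11%. For one-sided error on the rate-ratio scale the loss can be negligible (5.2-5.9% at ICC 0 in the second parametrisation).

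A reader might conclude that regional results are seriously anti-conservative whatever the setting. The documents do not support that. Size depends on CV, ICC, district counts and estimand, and for the sample rate ratio with intervention-only cluster effects the excess may be small or absent. The simulation covers IPT uptake. TB incidence inherits the same rule but was not simulated separately.

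**What to change.** In SAP sections 2 and 3, state the number of groups and districts per region and arm, and exempt the region strata from the N-2 rule. Then report regional rate ratios in one of three ways:

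- **Cluster-level t-test on the randomized groups.** In the Southwest this has 2 df, with a two-sided critical value of 4.303 against 2.365 (7 df) to 2.145 (14 df), a multiplier 1.8 to 2.0 times larger. Simulated size is 4.6-5.9% and coverage 94.0-95.3%.
- **Pooled variance.** Pool the intervention-arm variance over all 7 mini-collaboratives around their region means (7 - 3 = 4 df), pool the control-arm variance likewise, and use Satterthwaite df. Non-coverage was 4-6% in equal-size layouts and 2-3% in the smaller-group Southwest. It assumes similar variance across regions, which the differing calendar windows make open to question.
- **Descriptive reporting** without p-values.

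In every case drop the regional one-sided N-2 tests and the regional pair permutation test. The other group-level companion analyses need not all go.

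The cost is SAP wording, a few lines of code and a dated entry in the history of changes. The downside is wider regional intervals.
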